3.2 Power and sample size

To detect the 2-week difference in seated SBP (primary outcome) observed in the DASH-Sodium trial² (-9.53 mm Hg, standard deviation of 10.46, a type 1 error of 0.05 with 80% power), we need 20 people in each arm (total 40). We will recruit 45 participants to account for a 10% attrition rate. Effect size and variance for the other endpoints (especially OH) will be used to inform power calculations for subsequent proposals.

3.3 Secondary Pre-specified Subpopulations Analysis

We will repeat the primary analysis to compare subpopulations based on the following criteria:

1. Baseline antihypertensive use (yes vs no)
2. Baseline diabetes (yes vs no)
3. Sex (men or women)

We will fit general linear models including a subpopulation of interest as a main effect term and an interaction with treatment term. The interaction terms will be used to assess for effect modification by baseline characteristic. Note these analyses are contingent on having sufficient number of participants with and without baseline antihypertensive use.

Other stratified or subpopulations analyses based on baseline characteristics may be performed for hypothesis generation beyond the main study.

3.4 Sensitivity analyses

1. Models from the analyses specified above will be fit with and without adjustment for baseline seated blood pressure.
2. We will perform three separate on-treatment analyses: (i) participants who ate 25% or less of non-study foods during the low sodium intervention, (ii) participants whose estimated calorie intake was met or exceeded by the food provided through the low sodium intervention, and (iii) persons who did not change antihypertensive medications during the post-randomization study period
3. We will examine blood pressure (systolic and diastolic) using the last measurement alone.

4 Other outcomes

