## Design and Outcomes

This study is an individual-level, parallel, randomized clinical trial. Eligible participants will be randomized to low versus usual sodium meal plans for two weeks. Assessments will be made at the in-person baseline visit, one week telephonic interview and 2 week in person follow-up visit. This proposal will be executed in collaboration with Dietetic Services of the Jack Satter House (Revere), which is equipped with an industry-grade kitchen, chefs, and in-person dining as well as delivery services that collectively serve 255 residents. Further, the facility has private space for interviews and assessments. We plan to recruit 40 individuals (75% women).

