## **Interventions and Duration**

Interventions for this study include:

1. A low sodium diet
2. A usual sodium diet

A participant will be on one of these two intervention arms for a period of 2 weeks. The last study visit for each participant will occur on the last day of their study diet intervention.

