## **9 STATISTICAL CONSIDERATIONS**

### **9.1 General Design Issues**

This is an individual level, randomized, parallel-arm trial testing the primary hypothesis that a low sodium meal plan will reduced seated systolic blood pressure after about 14-days of feeding, compared to a typical sodium meal plan. For additional details please refer to our statistical analysis plan.

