### Sensitivity analyses

1. Models from the analyses specified above will be fit with and without adjustment for baseline seated blood pressure.
2. We will perform three separate on-treatment analysis: (i) participants who ate 25% or less of non-study foods during the low sodium intervention, (ii) participants whose estimated calorie intake was met or exceeded by the food provided through the low sodium intervention, and (iii) persons who did not change antihypertensive medications during the post-randomization study period

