### Analyses of other outcomes

- **Compliance:** Compliance will be quantified by (i) counts and proportion of participants who ate 25% or less of non-study foods during the low sodium intervention, (ii) counts and proportion of participants whose estimated calorie intake was met or exceeded by the food provided through the low sodium intervention. The data will be reported by treatment group and overall.
- **Secondary Endpoints:** We will examine the effect of the low sodium diet on the following additional outcomes, testing the null hypothesis that there is no difference in the following outcomes between the low sodium diet and usual sodium diet intervention. Continuous outcomes will be evaluated using linear regression to compare change between the 2 interventions arms with and without adjustment for baseline. We will examine the distribution of all variables. We will use linear regression for normally distributed outcomes and logistic regression for binary outcomes. Continuous variables with non-normal residuals will be log-transformed with effects reported as a % change.
  - Seated diastolic blood pressure
    - Continuous variable, normal distribution
  - Standing blood pressure
    - Continuous variable, normal distribution
  - Orthostatic hypotension
    - Binary variable, binomial distribution
  - Timed Up and Go Test
    - Continuous variable, normal distribution
  - Urinary sodium, potassium, and creatinine excretion
    - These may require log-transformation; anticipate continuous variables, normal distribution
  - Orthostatic symptoms
    - Binary variables (severe vs not), binomial distribution

**Handling of missing data:** We will employ a number of recommended strategies to prevent missing data:

- A simplified data collection schedule that minimizes participant burden;
- Intention-to-treat analysis that includes following participants according to the data collection schedule regardless of compliance with the study intervention;
- Frequent engagement with the participants through visit reminder calls or notes;
- A 24-hour phone number that participants can contact for questions and support;
- Contiguous windows of time during which specific follow-up visits are allowed;
- Monetary incentives to encourage enrollment and continued participation;
- Rigorous training of clinic staff emphasizing the importance of
  - Positive and warm interpersonal relationships between the participants and study staff

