4.1 Compliance

Compliance will be quantified by (i) counts and proportion of participants who ate 75% or more of study foods. The data will be reported by treatment group and overall.

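### On-treatment analyses (i) and (ii) and both protocol compliance measures are defined only for the low sodium diet, so a parallel trial has no rule for the usual-diet arm

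*SAP*

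**What the plan says.** The design is parallel. Protocol 9.1 states "This is an individual level, randomized, parallel-arm trial", and the synopsis (Interventions and Duration) adds "A participant will be on one of these two intervention arms for a period of 2 weeks".

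SAP 3.4 and the sensitivity analyses in protocol 9.5 list the same three on-treatment analyses:

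- Criterion (i) limits outside food. It keeps "participants who ate 25% or less of non-study foods during the low sodium intervention".
- Criterion (ii) concerns whether the meals supplied enough calories, and again refers only to the low sodium diet.
- Criterion (iii) concerns medication and names no diet. It keeps "persons who did not change antihypertensive medications during the post-randomization study period".

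The compliance paragraph in protocol 9.5 uses the definitions in (i) and (ii) for its two measures and then says "The data will be reported by treatment group and overall". SAP 4.1 has a single compliance measure that is not tied to an arm: "counts and proportion of participants who ate 75% or more of study foods".

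The primary analysis is intent-to-treat in both documents. Protocol 5.1 has every participant, in either arm, keep a daily food log.

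**The concern.** A usual-diet participant never receives the low sodium intervention, so criteria (i) and (ii) have no value for that person. Neither document says how the usual-diet arm enters these two analyses. The analyst would have to settle this after data exist, which a pre-specified plan is meant to prevent.

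If the choice were to filter the low sodium arm and keep every control, selected participants would be compared with unselected ones. Any link between compliance and blood pressure would then appear as a diet effect. The compliance report has a related problem: it is promised for both groups, but its definition covers one.

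**Working it through.** **1. Which rules are affected**

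| Rule | Tied to low sodium diet? | Can classify the usual-diet arm? |
|---|---|---|
| On-treatment (i), SAP 3.4 and protocol 9.5 | Yes | No |
| On-treatment (ii), same places | Yes | No |
| On-treatment (iii), same places | No | Yes |
| Both compliance measures, protocol 9.5 | Yes | No |
| Compliance measure, SAP 4.1 | No | Yes |

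Two of the three on-treatment criteria and both protocol compliance measures fail; criterion (iii) and SAP 4.1 do not.

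**2. Plan figures used for scale**

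SAP 3.2 gives a difference of 9.53 mm Hg, SD 10.46, type 1 error 0.05, power 80% and 20 per arm. The normal approximation is 2 × (1.960 + 0.842)² × 10.46² / 9.53² = 18.9, or 19 per arm. The t-test calculation gives 19.92, or 20 per arm. Then 40 / 0.9 = 44.4, or 45 recruited. The plan's figures reproduce. They do not bear on the wording problem but supply an SD and a reference effect.

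**3. Null bias if only the low sodium arm is filtered**

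Assumptions not in the documents: 30% of the arm is excluded; compliance correlates r = 0.2 to 0.4 with lower follow-up SBP; 10.46 is the SD of SBP at both times.

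Mean shift of the retained 70%, in SD units of compliance: φ(-0.524) / 0.70 = 0.497.

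(a) *Compliance unrelated to baseline SBP.* Baseline adjustment removes nothing, so bias = -r × 0.497 × 10.46:

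- r = 0.2: -1.04 mm Hg (11% of 9.53)
- r = 0.3: -1.56 mm Hg (16%)
- r = 0.4: -2.08 mm Hg (22%)

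(b) *Compliance equally related to baseline and follow-up SBP*, with correlation ρ = 0.5 to 0.7 between the two (assumed). The planned adjustment removes a share ρ, so bias = -r × 0.497 × 10.46 × (1 - ρ):

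- smallest: 1.04 × 0.3, giving -0.31 mm Hg
- largest: 2.08 × 0.5, giving -1.04 mm Hg

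(c) *Link wholly through baseline.* The follow-up correlation is r × ρ, and the adjustment removes ρ × r, so the bias is about 0.

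Simulation with 20 per arm, baseline-adjusted regression and no diet effect agrees with all three cases to within 0.05 mm Hg.

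**4. Size against sampling error**

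With 14 against 20 participants, SE = 10.46 × √(1/14 + 1/20) = 3.64 mm Hg. The case (a) bias is therefore 0.29 to 0.57 SE, and a nominal two-sided 0.05 test would reject about 6% to 9% of the time under the null.

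**5. Same filter in both arms**

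If compliance works alike in the arms, the simulated bias is within 0.04 mm Hg of zero. If 30% are excluded from one arm and 10% from the other (assumed), the factors are 0.497 and φ(-1.282) / 0.90 = 0.195. The residual, before baseline adjustment, is (0.497 - 0.195) × 10.46 × r = 0.6 to 1.3 mm Hg for r = 0.2 to 0.4. The two-arm filter reduces the bias but does not guarantee its removal.

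**6. Criterion (i) against SAP 4.1**

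If both percentages are shares of total intake, 25% or less non-study food and 75% or more study food are the same rule. If the SAP 4.1 percentage is a share of food supplied, a participant who leaves half the study food and eats nothing else passes (i) and fails SAP 4.1. Neither document states the denominator.

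**The case against.** The strongest reply is that this is leftover wording. Protocol 9.2.1 and the synopsis still speak of randomising to sequences, the compliance paragraph expects figures for both groups, and food logs exist in both arms. The authors may well have meant the filter for everyone. That stands as a reading of intent, and it means a reader should not infer that the plan states a comparison of selected compliers with an unfiltered control arm. The text is silent on the usual-diet arm. Silence still leaves the rule unusable, and the intended reading also requires the words to change.

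Four other points stand:

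- It would be too broad to say that all the on-treatment analyses are affected, because (iii) applies to both arms.
- A reader might infer that these analyses carry the robustness claim for the primary result. The explicit robustness statement in both documents concerns the missing-data analyses, and (i) and (ii) are two among several sensitivity analyses.
- Criterion (ii) asks whether the food provided met estimated calorie intake. That is adequacy of provision, not compliance, so a complier-selection model fits it poorly and it should not be folded into a single compliance rule.
- A contradiction between (i) and SAP 4.1 is not shown, because the denominators are undefined.

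The analyses already sit under a sensitivity heading, apart from the intent-to-treat analysis, so part of the needed labelling is present.

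**Conclusion.** The defect holds for on-treatment analyses (i) and (ii) in both documents and for the two protocol compliance measures. As written they cannot be applied to the usual-diet arm, and the compliance measures cannot be reported by group. This follows from the text and needs no assumption.

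The numerical consequence is conditional. It arises only if the low sodium arm alone is filtered, and it rests on an assumed 30% exclusion and r of 0.2 to 0.4: about -1.0 to -2.1 mm Hg at most, about -0.3 to -1.0 with equal relation to baseline and follow-up SBP, and near 0 if the link runs through baseline. Against a standard error of about 3.6 mm Hg this is modest, so the documents do not support saying that the analysis would manufacture a diet effect. The primary estimate and test are untouched. The wording should be corrected before analysis, but it does not threaten the main result.

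**What to change.** - In SAP 3.4, and in the sensitivity and compliance paragraphs of protocol 9.5, replace the reference to the low sodium intervention in (i) and (ii) with *the assigned study diet, in both arms*. Leave (iii) as it is.
- Keep (ii) as a separate analysis of the adequacy of the food provided.
- Align the food-intake criterion in (i) with the SAP 4.1 measure and state one denominator, so that reported compliance describes the on-treatment set.
- State that these analyses are non-randomised and supportive, because selection bias can remain when the arms comply differently.

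The cost is wording plus some precision. Daily food logs already cover both arms, so no new data are needed. Fewer participants from both arms enter the on-treatment sets: by normal approximation, power for 9.53 mm Hg at the 0.05 level falls from 0.82 with 20 per arm to 0.78 with 18, 0.70 with 15 and 0.53 with 10.

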### **5.2 Handling of Study Interventions**

Diet and menu development for both lower sodium and usual sodium diets was done by the study dietitians, keeping the diets similar in types of foods and macronutrient content. Diet selections are also isocaloric, based on the Mifflin St. Jeor calculation for each individual's energy expenditure and BMI.

Ingredients for the dietary intervention will be procured by [name], head chef at Jack Satter House and [name], director of the culinary and nutrition services at Hebrew SeniorLife and Jack Satter House. The ingredients will be stored in the kitchen at the

Jack Satter House where chef [name] will prepare all the meals each day. Cost of these meals will be paid by the funds from the study and have been subsidized by the department of culinary and nutrition services. During the intervention period, each day chef [name] will prepare breakfast, a boxed lunch a two snacks that will be delivered to the participants at their apartment by chef [name] and dining room manager [name]. Dinner will be prepared separately and will either be delivered to the study participant's apartment or will be picked up in a box with an option of consuming the dinner in the dining room.

Participants will complete a daily food log, during the 2 week intervention period, and palatability questionnaires at study visits, to track compliance with and tolerability of the diet. Participants are blinded to their diet randomization and are asked not to discuss their study food with others during the course of the intervention.

Meals for both the study arms will be kept as similar as possible except for the sodium content.

Based on participant's feedback, the protocol was changed and any participant who reported not consuming their meals via daily food logs were contacted to confirm if their meal portions were adequate. This information was also collected at the 1-week telephone visit for all participants. Portion sizes were altered based on participant's preference. Furthermore, as a safe guard, participants who reported to be diabetic were contacted and their portion sizes and or carbohydrate levels of their meals were adjusted based on participant preference.

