#### Screening

**Visit 1. [Screening (SV) and initial baseline visit (BV1a)]:** Eligible participants will be undergo written informed consent. Questionnaire based information on demography, self-reported physical activity and medication list will be obtained for eligible participants as part of the initial baseline visit. Assessments of orthostatic hypotension, MoCA and seated blood pressure will be done at this visit to check for eligibility of the participant. Weight and height will be measured to calculate targeted caloric intake. This information will be needed in advance to prepare meals for the participants.

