#### Meal size concerns

Participants with patterns of inadequate food quantity or conversely undereating due to the provision of too much food will be contacted for adjustments to their meal size. In particular, we will reach out to participants with known glucose impairments to ensure the appropriateness of their meal size with plans for adjustments based on feedback the preceding 3-4 days.

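### On-treatment criterion (ii) asks whether enough food was provided, not whether it was eaten, so it does not identify participants who were on treatment

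*SAP*

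**What the plan says.** SAP 3.4 lists three separate on-treatment analyses. The second is restricted to "participants whose estimated calorie intake was met or exceeded by the food provided through the low sodium intervention". The sensitivity analyses in Protocol 9.5 carry the same rule. Protocol 9.5, Analyses of other outcomes, also uses it as one of two compliance measures: "counts and proportion of participants whose estimated calorie intake was met or exceeded by the food provided through the low sodium intervention". SAP 4.1 does not repeat that count. It measures compliance by the proportion of participants who ate at least 75% of study foods.

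Neither document defines *estimated calorie intake*. The nearest description is how rations are set. At screening, "Weight and height will be measured to calculate targeted caloric intake", and Protocol 5.2 says: "Diet selections are also isocaloric, based on the Mifflin St. Jeor calculation for each individual's energy expenditure and BMI".

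Portions could change once feeding had begun. Protocol 5.2 says that "any participant who reported not consuming their meals via daily food logs were contacted to confirm if their meal portions were adequate", and then: "Portion sizes were altered based on participant's preference". It adds that "participants who reported to be diabetic were contacted and their portion sizes and or carbohydrate levels of their meals were adjusted". The meal-size text in Protocol 7.3 covers both directions: "Participants with patterns of inadequate food quantity or conversely undereating due to the provision of too much food will be contacted for adjustments".

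**The concern.** An on-treatment analysis should keep people who took the assigned treatment and set aside those who did not. Here the treatment is a diet defined by sodium per kcal, so being on treatment means eating the study food and little else. Criterion (ii) looks at what left the kitchen. It cannot tell a person who ate the diet from one who left it on the tray.

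It can also err the other way. A smaller portion, fully eaten with nothing added, still delivers the assigned sodium density, yet it can fail the rule. Portion changes come after randomization and are prompted in part by logged under-eating. They also involve participants with diabetes, a pre-specified subgroup in SAP 3.3. Exclusions that follow from them would not be random.

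Two things are at stake. A result labelled on-treatment may be read as support among people who complied, when compliance was not measured. And the protocol would report food provision as compliance, which is part of Feasibility Aim 1.

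**Working it through.** **The plan's own figures.** The documents give no figure for this criterion. The arm size used below is the SAP 3.2 figure of 20 per arm, which reproduces. With a difference of 9.53 mm Hg, SD 10.46, two-sided 0.05 and 80% power, the normal formula 2 × (10.46 × (1.960 + 0.842) / 9.53)² gives 18.9. The two-sample t calculation gives 19.9, hence 20. Allowing for attrition, 40 / 0.9 = 44.4, hence 45.

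**Reading A: the calorie term is the formula target (Protocol 5.2 and 6.2.1).** Set the target to 1.00. The rule passes a person if provided / target ≥ 1.00. The last column applies the SAP 4.1 threshold to the share of the served portion that was eaten. Eating levels and sizes of cut are assumed, and the target is taken as not re-estimated after a cut.

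| Portion cut | Share of served food eaten | Provided / target | Criterion (ii) | Eaten / target | 75% of served food eaten |
|---|---|---|---|---|---|
| none | 100% | 1.00 | pass | 1.00 | pass |
| none | 75% | 1.00 | pass | 0.75 | pass |
| none | 50% | 1.00 | pass | 0.50 | fail |
| none | 25% | 1.00 | pass | 0.25 | fail |
| 10% | 100% | 0.90 | fail | 0.90 | pass |
| 10% | 25% | 0.90 | fail | 0.225 | fail |
| 25% | 100% | 0.75 | fail | 0.75 | pass |

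On this reading, status follows portion size and does not respond to intake.

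**Reading B: the calorie term is intake estimated from the food log, non-study foods included.** The rule passes a person if logged intake ≤ provided, with provided = 1.00. These cases are again illustrative:

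- Eats 25% of the ration and nothing else: 0.25 ≤ 1.00, pass.
- Eats half the ration and replaces the rest with non-study food: 0.50 + 0.50 = 1.00 ≤ 1.00, pass.
- Eats the whole ration plus a further 10% of non-study food: 1.10 > 1.00, fail.

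The rule now responds to intake, but only to excess. It keeps the person who ate little and the person who replaced half the diet.

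**How many people this touches.** The share with reduced portions is not given. On Reading A, with a 20-person low sodium arm and every reduction taking the ration below target, the number passing is 20 × (1 − f), where f is the assumed share reduced:

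| f | 0 | 5% | 10% | 20% | 30% | 50% |
|---|---|---|---|---|---|---|
| Number passing | 20 | 19 | 18 | 16 | 14 | 10 |

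The low sodium arm is the denominator because the criterion is worded for that intervention. The usual-sodium arm has no stated rule.

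**The case against.** The strongest reply is that the calorie term is undefined and the logged-intake reading has some use. Protocol 5.4 asks participants to log non-study foods, and someone whose total exceeds the ration has supplemented the diet, which is real contamination in a sodium feeding trial. This stands: on that reading, passing is not automatic. It does not rescue the rule, because under-eaters and substituters are still kept.

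A reader might infer that nearly everyone would pass, or that the protocol's compliance figure would be close to 100%. The documents do not support this. It needs Reading A together with few reductions, and no number of changed portions is given.

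A reader might also infer that the only people who can fail are those who asked for smaller meals. That is too narrow. Changes followed study contact as well as preference, included carbohydrate adjustments for participants with diabetes, and could be increases. The Day 7 telephone visit also asks whether the diet meets caloric needs. If that answer feeds the criterion, which the text does not say, someone who found the food insufficient could fail with no reduction at all.

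The consequence is limited. This is one of three on-treatment sensitivity analyses, criterion (i) does address what was eaten, and no decision rule depends on (ii). SAP 4.1 has already dropped the provision count, and Feasibility Aim 1 also names urine sodium and palatability questionnaires. All of that stands, and it keeps the point modest.

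**Conclusion.** The concern holds as a defect of definition. Criterion (ii) has no term for study food eaten. Read as the formula target, it is met by construction at the start whatever the participant eats, and a person whose portion was later reduced below target can fail after eating everything. Read as logged intake, it removes those who ate more than was supplied and keeps those who ate very little. On neither reading does it identify participants who were on treatment. Protocol 9.5 also reports it as compliance, which SAP 4.1 does not.

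Its numerical size cannot be fixed from the documents: the counts above rest on assumed shares of reduced portions, and the failure after full consumption assumes the target is not re-estimated. The failure to separate eaters from non-eaters on unaltered rations does not depend on those shares. It would be wrong to infer that the main result is compromised, because the intent-to-treat primary analysis does not use this criterion.

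**What to change.** - In SAP 3.4 and the sensitivity analyses of Protocol 9.5, replace criterion (ii) with the SAP 4.1 threshold: at least 75% of study foods eaten, taken from the daily food log, relative to the portions actually served after any change. Apply it in both arms and report the number qualifying in each. Criterion (i) continues to cover non-study foods.
- Align the compliance text of Protocol 9.5 with SAP 4.1. Delete the calorie-provision count, or keep it under the label *adequacy of portions supplied* with the calorie term defined.
- Do not substitute a rule on the share of calories consumed that came from study food. Someone who eats 10% of the ration and nothing else scores 0.10 / 0.10 = 100% and passes, and such a rule largely repeats criterion (i).

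The cost is wording in two documents and a calculation from daily food logs and meal records the study already plans to hold. The downsides are that food logs are self-reported and approximate, and that the on-treatment set may be smaller. The set would still be selected after randomization, so it should stay a sensitivity analysis.
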